5.1 Inclusion Criteria

Age

1. Patients must be ≥ 18 years of age at the time of signing the informed consent.

Type of Patient and Disease Characteristics

2. Patients who had a kidney transplant performed ≥ 28 days prior to enrollment.
3. BKV, based on the following criteria (both criteria a and b must be met):
 - a. Any positive whole blood or plasma BK viral load at a local laboratory obtained ≤ 90 days before the start of screening.
 - b. Confirmation of BK viremia of 350 copies/mL – 10,000,000 copies/mL as determined by the central laboratory at screening.
4. At least 1 identified, suitably matched PSL cell line for infusion is available.

Sex

5. Male and/or female

Contraceptive use by men and women should be consistent with local regulations regarding the methods of contraception for those participating in clinical studies.

- a. Male patients:

Male patients are eligible to participate if they agree to the following during the study treatment period and for at least 90 days after the last dose of study treatment:

- Refrain from donating sperm

PLUS, either:

- Be abstinent from heterosexual intercourse as their preferred and usual lifestyle (abstinent on a long term and persistent basis) and agree to remain abstinent

OR

- Must agree to use contraception /barrier as detailed below
 - Agree to use a male condom and should also be advised of the benefit for a female partner to use a highly effective method of contraception as a condom may break or leak when having sexual intercourse with a woman of childbearing potential (WOCBP) who is not currently pregnant b. Female patients:
 - A female patient is eligible to participate if she is not pregnant or breastfeeding, and 1 of the following conditions applies:

- She is a woman of non-childbearing potential (WONCBP) as defined in [Section 10.4.1](#)

OR

- She is a WOCBP and using an acceptable contraceptive method as described in [Section 10.4.2](#) during the study treatment period and for at least 90 days after the last dose of study treatment. The Investigator should evaluate the potential for contraceptive method failure (eg, noncompliance, recently initiated) in relationship to the first dose of study treatment.
- A WOCBP must have a negative highly sensitive serum pregnancy test within 21 days before the first dose of study treatment, see [Section 8.2.5](#).
- Additional requirements for pregnancy testing during and after study treatment are located in [Section 8.2.5](#).

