8.1.1 Viral Load

In patients with concomitant viral infections at the time of treatment, peripheral blood and, where relevant, urine, will be monitored for BKV, CMV, AdV, EBV, JCV, and/or HHV-6 viral load (see [Section 1.3](#)). Resolution of viral infection will be defined as a return to undetectable as defined by the assay used and complete resolution of clinical signs and symptoms as determined by the Investigator. Viral load will be quantitated using polymerase chain reaction assays.

Samples for viral sequence/genotype will be collected on all patients as indicated in [Section 1.3](#).

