After the first 3 doses, patients who have undetectable BK plasma viral load at 2 or more consecutive assessments at least 2 weeks apart will discontinue PSL infusions. If a patient's viral load becomes undetectable, such a patient may be followed every 14 days for study evaluations as per the Schedule of Activities. Patients will not be permitted to receive a subsequent infusion of PSL if they develop new onset graft vs host disease (GVHD) \geq Stage 1 or cytokine release syndrome (CRS) > Grade 2 at the proposed time for infusion of any subsequent dose.

A summary of study design is shown in [Figure 1](#).

2.2.2 *Study Drug*

PSL is a third-party, donor-derived, "off-the-shelf," virus-specific T cell product with specificity for BKV, AdV, CMV, EBV, and HHV-6 (with additional cross-reactive specificity for JCV) that is cryopreserved and ready for immediate use. Cryopreservation media (without cells) will serve as the placebo and will be identical in volume and appearance when administered.

2.2.3 *Sample Size Determination*

No formal sample size determination was made for this study, whose primary endpoint is safety and tolerability. Approximately 60 patients will be randomized at approximately 38 clinical sites. Patients (n=20 in each arm) will be randomized to receive PSL (administered at a dose interval of every 14 or 28 days after 3 initial weekly doses) or placebo.

Patients will be stratified [REDACTED]

[REDACTED] A minimum of 6 patients must be enrolled in each stratum, but the remaining patients can be enrolled in either stratum.

Figure 1. Study Flow Chart

b Administrative interim analysis #1 will be performed by the Sponsor when 12 patients in Stratum 1 have completed 8 weeks in the study. Administrative interim analysis #2 will be performed when 30 patients have completed 8 weeks in the study. Interim analyses may be omitted or added at the discretion of the Sponsor to allow for long term planning, and to assess ending the study or either arm early.

Abbreviations: BKV=BK virus; Q=every; S/P=status post

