3.4.2 Exploratory Efficacy Endpoints

Observed results, change from Baseline, and percent change from baseline for eGFR estimated by MDRD and creatinine will be summarized by visit using descriptive statistics.

Donor specific anti-HLA antibodies (DSA) (yes/no) will be summarized by visit using descriptive statistics.

Resolution of viremia will be generally defined as achieving a post-baseline viral load measure below the lower limit of quantification (<LLOQ) for that viral assay. The number of patients with resolution for each virus (BKV, CMV, EBV, AdV, JCV, and/or HHV-6) will be summarized by visit and at any visits. In addition, the proportion of patients reaching at least 1 log10 reduction or <LLOQ in BK viral load post infusion will be summarized by visit and at any visits.

LLOQ values for the viruses of interest are:

BKV Viral Load (Copy/mL): LLOQ = 156

Non-BK Target Viruses:

ADV Viral Load (Copy/mL): LLOQ = 32

CMV Viral Load (Copy/mL): LLOQ = 65.6

EBV Viral Load (Copy/mL): LLOQ = 37

HHV-6 Human Herpesvirus 6 (Copy/mL): LLOQ = 110

JCV JC Virus (IU/mL): LLOQ = 76

Time-to-event endpoints will be summarized using the Kaplan-Meier method. Number of patients with events and number of patients censored and reason of censoring will be presented along with estimate for the median time (days) and its 95% CI. Time-to-event will be presented using Kaplan-Meier plots.

Time to resolution of BK viremia will be calculated as starting at randomization for patients with detectable virus and ending at the first undetectable viral load (i.e., <LLOQ). Patients who discontinued from the study early or deceased before they are observed to have achieved resolution will be censored at the last assessment date for this endpoint.

For patients who reach the resolution of BK viremia, time to reappearance of BK viremia (duration of viral remission) will be calculated as starting at the first assessment with undetectable viral load and ending at the first detectable viral load (confirmed with 2 consecutive measures at least 8 days apart, or end of study if only one measure is available). Patients not demonstrating the reappearance of viremia would be censored on the date of the latest assessment for this endpoint. Patients who discontinued from the study early or deceased before they are observed to have will be censored at the last assessment date for this endpoint.

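### For patients entering near the 350 copies/mL floor, any-visit BK resolution, time to resolution and remission start rest on one unconfirmed value below 156 copies/mL

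*SAP*

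**What the plan says.** **Definition.** SAP 3.4.2 treats viremia as resolved on "achieving a post-baseline viral load measure below the lower limit of quantification (<LLOQ) for that viral assay". The limit for BK virus is given as "BKV Viral Load (Copy/mL): LLOQ = 156". No confirming sample is asked for.

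**Uses.** The number of patients with resolution "will be summarized by visit and at any visits". Time to BK resolution runs from randomization to the first value below the limit, and duration of remission starts at that same value.

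**Opportunities.** Protocol 1.3 and SAP Appendix B schedule BK viral load at Weeks 2, 4, 6 and so on to Week 24, which is 12 post-baseline visits.

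**Entry floor.** Protocol 5.1 requires "Confirmation of BK viremia of 350 copies/mL" or more at the central laboratory, up to 10,000,000.

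**Rules elsewhere that ask for two values.** Infusions stop after "undetectable BK plasma viral load at 2 or more consecutive assessments at least 2 weeks apart" (SAP 2.2.1; also Protocol 9.5.1.1). Reappearance of BK viremia in SAP 3.4.2 must be "confirmed with 2 consecutive measures at least 8 days apart", with an exception when only one measure is left at the end of study. Protocol section 3 and SAP 2.3.3 put the spacing for reappearance at 2 weeks instead of 8 days.

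**Protocol definition.** Protocol 8.1.1 defines resolution as a "return to undetectable as defined by the assay used" together with full resolution of clinical signs and symptoms. The SAP equates undetectable with below the LLOQ and drops the clinical part.

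**The concern.** The floor for entry and the threshold for clearance are close together. A patient with a stable load just above 350 copies/mL has 12 chances to give one low reading, and one is enough. Such a patient counts as resolved at any visit, contributes an event to the Kaplan-Meier curve for time to resolution, and enters the remission analysis. If the next two readings are back above the limit, the same patient then contributes a relapse after one visit.

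The rule is the same in every arm, so the expected effect is to raise the placebo and PSL rates together and shrink the difference between them. SAP 3.4 presents efficacy by stratum, so the artefact would gather in the lower viral load stratum. With about 20 patients per arm, a few false clearances can visibly move a proportion or a median.

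**Working it through.** **Inputs from the documents.** LLOQ 156 copies/mL; entry floor 350 copies/mL; 12 post-baseline BK visits; 20 patients per arm, so 40 pooled PSL against 20 placebo. The sample size has no stated response rates or power, so there is no figure of the plan's own to reproduce here.

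**Assumption.** The documents give no assay or within-patient SD. I take the total log10 SD (assay plus day-to-day) from 0.10 to 0.50.

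**Step 1, the gap.** 350/156 = 2.24, and log10(2.24) = 0.351. A fall of 0.35 log10 from the floor counts as resolution.

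**Step 2, one visit.** For a patient whose true load stays constant, the chance of a reading below 156 is p = Φ(−gap/SD). At SD 0.20, p = Φ(−0.351/0.20) = 4.0%.

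**Step 3, any of 12.** With independent visits this is 1 − (1 − p)^12. At SD 0.20: 1 − (1 − 0.0397)^12 = 38%.

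**Step 4, two consecutive of 12.** This is an exact recursion with states a (last reading not below), b (last reading below, unconfirmed) and c (confirmed), starting at a = 1. At each visit a becomes (a + b)(1 − p), b becomes a·p, and c becomes c + b·p. The answer is c after 12 visits.

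Constant true load of 350 copies/mL, independent visits:

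| SD (log10) | One given visit | Any of 12 | Two consecutive |
|---|---|---|---|
| 0.10 | 0.02% | 0.3% | 0.0% |
| 0.15 | 1.0% | 11% | 0.1% |
| 0.20 | 4.0% | 38% | 1.7% |
| 0.25 | 8.0% | 63% | 6.4% |
| 0.30 | 12% | 79% | 14% |
| 0.50 | 24% | 96% | 43% |

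**Step 5, correlated visits.** With first-order autocorrelation of 0.5 between visits (400,000 simulated paths), any of 12 against two consecutive is 32% against 7% at SD 0.20, and 66% against 28% at SD 0.30.

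**Step 6, higher loads.** With independent visits, any of 12 at 500 copies/mL is 7% (SD 0.20) and 43% (SD 0.30). At 1,000 it is 0.03% (SD 0.20) and 4.2% (SD 0.30), though 48% at SD 0.50. At 2,000 it is 0.1% (SD 0.30). At 10,000 it is at most 0.2% even at SD 0.50.

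**Step 7, one-visit remissions.** After a false clearance at 350, the next two readings are both at or above 156 with probability (1 − p)². That is 0.9603² = 92% at SD 0.20 and 0.8790² = 77% at SD 0.30, again with independent visits.

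**Step 8, dilution (illustration only).** Assume true resolution rates of 20% (placebo) and 50% (pooled PSL), a quarter of non-clearers sitting at 350, and SD 0.20. Noise converts 0.25 × 0.385 = 9.6% of non-clearers. The observed rates become 0.20 + 0.80 × 0.096 = 27.7% and 0.50 + 0.50 × 0.096 = 54.8%, so the difference falls from 30 to 27 points.

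**The case against.** The strongest reply is that little rides on this. The resolution endpoints are exploratory, Protocol 9.1 plans no formal hypothesis testing, and SAP 3.4.2 is descriptive. The key secondary endpoint, change in BK viral load, does not use the definition. The resolution endpoint listed in Protocol section 3 is the proportion at 8 weeks. The by-visit table supplies it with noise from a single visit: 4% at SD 0.20 and 12% at SD 0.30, even at a constant 350. All of this stands and limits the weight of the point.

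A second reply is that the numbers depend on an assumed SD and a worst-case patient. This also stands. At SD 0.10 the effect is negligible. Independence makes two-value confirmation look better than it is: with correlation 0.5 the residual at SD 0.20 is 7%, not 1.7%. A load held at exactly 350 for 24 weeks is artificial, since immunosuppression reduction is permitted in all arms.

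A reader might also infer that resolution is the only BK state in the plan that needs no confirmation. The documents do not support that. A rise to 10,000 copies/mL or more counts whether or not it persists, new or recrudescent infection is defined by onset of viremia alone, the response of a 1 log10 fall or a value below the LLOQ needs one reading, and reappearance can rest on one measure at the end of study. The contrast is with two rules only: the infusion-stop rule and the main reappearance rule. The first governs exposure, so its stricter standard need not carry over to an endpoint.

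**Conclusion.** The point holds for patients entering near the floor and for three summaries: the any-visit proportion, time to resolution and the start of remission. For a true load of 350 copies/mL, the chance of a false clearance over 12 visits runs from 0.3% (SD 0.10) through 38% (SD 0.20) to 79% (SD 0.30) under independence, and is 32% and 66% at the last two SDs with correlation 0.5. Requiring two consecutive values lowers these figures substantially but does not remove them.

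A reader might infer that noise inflates clearance across the whole trial. The figures do not show that. Entry extends to 10,000,000 copies/mL, the effect is about 4% or less at 1,000 copies/mL up to SD 0.30, and the baseline mix is unknown, with only 6 patients guaranteed per stratum. Nor does the definition favor PSL by construction, because it is identical in all arms. This is a worthwhile, inexpensive improvement to exploratory summaries. It does not threaten the primary or key secondary analysis.

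**What to change.** Before unblinding, amend SAP 3.4.2 as follows.

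- For the any-visit proportion, time to BK resolution and the start of remission, define BK resolution as below the LLOQ at two consecutive central-laboratory assessments, dated at the first.
- State one minimum spacing, reconciling the 2 weeks in Protocol section 3 and SAP 2.3.3 with the 8 days in SAP 3.4.2. The visit windows matter here: with ±3 days in Period 1, adjacent two-weekly visits can be 14 − 3 − 3 = 8 days apart, so a strict 14 days would reject some in-window pairs. The ±7 days in Period 2 allow even closer pairs.
- Report separately the first clearances that cannot be confirmed: at Week 24, before dropout, or with the confirming visit missed.
- Keep the single-value definition for the by-visit table, including Week 8, and as a sensitivity analysis for the other summaries.
- Reconcile the SAP's use of the LLOQ with Protocol 8.1.1, which asks for an undetectable result plus clinical resolution.

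The cost is SAP wording and programming. No samples, visits or treatment rules change. The downside is somewhat fewer resolution events.

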4 STUDY DESIGN

4.1 Overall Design

This is a Phase 2, multicenter, randomized, double-blind, placebo-controlled, multiple dosing interval, 2-period study of the safety, tolerability and efficacy of adoptively transferred PSL virus-specific T cells in kidney transplant recipients with BK viremia.

This study is comprised of 2 periods. Period 1 includes a 2-week window for screening assessments followed by a 12-week treatment period for eligible patients. Period 2 consists of a 12-week follow-up. Overall, the total duration of patient participation in the study is approximately 26 weeks (2 weeks for screening, 12 weeks of treatment, and 12 weeks of follow-up). The overall enrollment period is anticipated to be approximately 12 months.

The protocol defines standardized consensus guidelines for the type of immunosuppression reduction in order to systematize the approach to immunosuppression reduction across sites (Appendix 7, [Section 10.7](#)). Administration of PSL in the active arms of the study may result in fewer patients meeting the criteria for initiation or intensification of immunosuppression reduction according to the protocol at their institution than in the placebo arm of the study, and changes to each patient's immunosuppression will be monitored.

Patients who meet all of the inclusion criteria and none of the exclusion criteria will be randomized to receive PSL or placebo infusions. Patients will be stratified [REDACTED]

Patients will be monitored following randomization for safety, BK viral load, renal function, and immune function, including modification of immunosuppression reduction.

Patients will receive infusions of either PSL or placebo for 12 weeks. The specific PSL cell line for infusion will be selected [REDACTED]

[REDACTED]. Cryopreservation media (without cells) will serve as the placebo and will be identical in volume and appearance upon administration. All infusions will be administered intravenously (IV) (via peripheral or central line) over approximately [REDACTED] as a slow push. Patients will receive the same dose for all infusions.

The study will consist of 3 treatment arms. To maintain the blind, all patients will receive an infusion (either PSL or placebo) [REDACTED]

The treatment arms and associated infusions for Cohort A are as follow:

- 

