4.2 Scientific Rationale for Study Design

Even with the best current treatments (principally immunosuppression reduction), many centers report allograft nephropathy, rejection, and graft failure more commonly in patients with BK viremia than in those without ([Favi 2019](#), [El-Husseini 2019](#), [Sawinski 2015](#)). The unmet medical need in BK virus nephropathy is reflected in the continued use of (ineffective) antiviral treatments such as leflunomide, cidofovir, intravenous immunoglobulin G, and levofloxacin concurrently with immunosuppression reduction ([Bruminhent 2019](#)).

PSL multivirus-specific T cells target BK virus infected cells, and thus offer a way to lower viral load in BK viremic kidney transplant recipients at risk for BK nephropathy. To date, immunosuppression reduction is the only therapy that has succeeded in lowering BK viral load, and even it has had limited success and can lead to increased risk of rejection and/or production of donor-specific antibodies. This proof-of-concept study will also identify the dosing interval for virus-specific T cell infusions needed to lower viral load in kidney transplant recipients on continued immunosuppression and potentially limit the damage caused by BK virus replication in the kidney allograft.

The use of placebo in this clinical study is justified for the following reasons:

- 1) A placebo control group is required to provide an objective, contemporaneous assessment of the therapeutic effects and AE profile of PSL.
- 2) The use of an active control group in the study is not feasible since there are no approved, efficacious antiviral therapies for the treatment of BKV infections.

3) Investigators are permitted to administer standard of care immunosuppression reduction as per the algorithm included in Appendix 7 ([Section 10.7](#)).

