6.8 Concomitant Therapy

All medications, including transplant immunosuppression, used within 30 days before screening will be recorded. All concomitant medications and concurrent therapies will be documented as

indicated in [Section 1.3](#). Dose, route, unit frequency of administration, indication for administration, and dates of medication will also be captured in source documents and on the appropriate eCRF.

Clinically available (ie, not investigational) antiviral agents prescribed for other infections, such as foscarnet and ganciclovir to treat CMV, are allowed. Data on their use will be collected along with other concomitant medications.

Standard of care immunosuppression reduction is permitted as per the guidelines for the type of immunosuppression reduction that are provided in Appendix 7 ([Section 10.7](#)). The typical immunosuppression regimen for kidney transplant patients, which includes a calcineurin inhibitor, an anti-metabolite, commonly mycophenolate mofetil or mycophenolic acid, with or without low dose prednisone, is included in Section 10.7, [Figure 2](#). If a patient's immunosuppression regimen includes sirolimus or everolimus, a change in these agents based on BK viral load is not usually made; for this reason they are not included in [Figure 2](#), and patients taking these medications who require changes in dose of their sirolimus or everolimus will require discussion with the Medical Monitor. These guidelines should be followed in order to standardize the approach to immunosuppression across sites. Administration of PSL in the active arms of the study may result in fewer patients meeting the criteria for modification of immunosuppression reduction according to the protocol at their institution than in the placebo arm of the study, and changes to each patient's immunosuppression will be monitored and may be summarized as an exploratory endpoint.

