10.7 Appendix 7: Modification of Immunosuppression

NOTE: *Viral load determinations that would lead to changes in immunosuppression (red boxes) should be repeated immediately upon receipt to confirm that action should be taken as indicated.

- a If MMF has already been reduced or discontinued more than 28 days prior, proceed to the next step in the algorithm. Other variations from the algorithm require consultation with, and approval by, the Sponsor's Medical Monitor.
- b Triple Immunosuppression: low-dose oral steroids, MMF, and calcineurin inhibitor.
- c Double Immunosuppression: MMF and calcineurin inhibitor.

Abbreviations: AST = American Society of Transplantation; KDIGO = Kidney Disease: Improving Global Outcomes; MMF = mycophenolate mofetil; PCR = polymerase chain reaction; PI = Principal Investigator (ie, Investigator); Q = very; VL = viral load

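### Does the SAP need a table that links BK viral response to immunosuppression reduction in all patients?

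*SAP*

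**What the plan says.** **ISR as background care.** Protocol 4.2 holds that "immunosuppression reduction is the only therapy that has succeeded in lowering BK viral load, and even it has had limited success", and also that "Investigators are permitted to administer standard of care immunosuppression reduction as per the algorithm included in Appendix 7". Protocol 4.1 expects a possible difference between arms: "Administration of PSL in the active arms of the study may result in fewer patients meeting the criteria for initiation or intensification of immunosuppression reduction". On reporting, Protocol 6.8 commits only to this: changes to each patient's "immunosuppression will be monitored and may be summarized as an exploratory endpoint".

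**Viral response.** SAP 3.4.1 and 3.4.2 summarise BK viral load, change, AUC, resolution and a responder proportion ("the proportion of patients reaching at least 1 log10 reduction or <LLOQ in BK viral load post infusion will be summarized by visit"). SAP 3.1.5 analyses data as observed. SAP 3.4 uses the ITT population by default and splits tables by stratum and treatment group. No summary is split by, or censored at, ISR.

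**ISR in the SAP.** Section 3.3.6 defines a dose reduction as a cut of 50% or more from the Baseline dose. Section 3.4.2 repeats that threshold and adds a list of counted drugs, with steroids, leflunomide and IVIG excluded. Table 1 has a Yes/No row for ISR. Section 3.4.3 counts the agents used and lists doses and dose changes by patient. The only endpoint holding both elements is the 3.4.2 composite: a rise to 10,000 copies/mL or more, or ISR, among patients who screened below 10,000.

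**The concern.** Appendix 7 of the protocol ties immunosuppression changes to viral load results, so ISR is a post-randomisation event that follows from the outcome and may also change it. If placebo patients have their doses cut more often and the cuts work, some placebo responses are owed to ISR. The observed difference would then understate what PSL does without ISR. The planned tables would show how many patients per arm had ISR and how many responded, but not whether these were the same patients. The either/or composite cannot answer that, and it leaves out everyone who screened at 10,000 or more, although eligibility runs to 10,000,000. A link made later from the listings would need choices, chiefly on the order of ISR and response, that could be made after unblinding.

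There are two side issues. Section 3.3.6 has no drug list, so read alone it could count a steroid taper that 3.4.2 excludes. And cuts made before Baseline escape the flag, although Appendix 7 foresees them: "If MMF has already been reduced or discontinued more than 28 days prior, proceed to the next step in the algorithm".

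**Working it through.** The plan gives no figure to reproduce here. The documents supply 20 patients per arm (Protocol 9.2; 3 x 20 = 60, so pooled PSL is 40) and a stratum minimum of 6 (SAP 2.2.3). Every ISR rate, response rate and ISR effect below is an assumption.

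**1. Shift in the response difference.** With the same ISR effect in both arms:

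shift = (ISR rate on placebo - ISR rate on PSL) x (response rate with ISR - response rate without ISR)

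- 0.10 x 0.10 = 0.01, or 1 point
- 0.30 x 0.30 = 0.09, or 9 points
- 0.40 x 0.40 = 0.16, or 16 points

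**2. Shift in mean log10 viral load.** With an ISR effect e that is equal in both arms, shift = (pC - pT) x e, where pC and pT are the ISR rates on placebo and PSL.

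- 40% vs 20%: 0.20 x 0.3 = 0.06 and 0.20 x 1.0 = 0.20
- 30% vs 20%: 0.10 x 0.3 = 0.03 and 0.10 x 1.0 = 0.10
- Equal rates: 0
- Unequal effects (0.5 on placebo, 1.0 on PSL): 0.4 x 0.5 - 0.2 x 1.0 = 0, and 0.3 x 0.5 - 0.2 x 1.0 = -0.05

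The direction is therefore not fixed. In the case the protocol expects (more ISR on placebo, similar effect in both arms), the observed contrast is conservative for PSL.

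**3. What the margins leave open.** With n patients, r responders and i patients with ISR, the overlap lies between max(0, r + i - n) and min(r, i).

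- Placebo, n = 20, r = 8, i = 8: 0 to 8, so 0-100% of responders
- Pooled PSL, n = 40, r = 20, i = 8: 0 to 8, so 0-40% of responders

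These are the limits that two margins always leave. They show that the link is not tabulated, not that a planned result is wrong.

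**4. Scoring ISR as non-response.** Take the same counts.

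- As observed: 20/40 - 8/20 = 50% - 40% = +10 points
- ISR-free response on placebo: (8 - 8)/20 to (8 - 0)/20 = 0-40%
- ISR-free response on PSL: (20 - 8)/40 to (20 - 0)/40 = 30-50%
- Difference: 30 - 40 = -10 to 50 - 0 = +50 points

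Such an endpoint penalises the arm with more ISR, so it can overstate PSL where the observed contrast understates it.

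**5. Precision of a plain cross-count.** Assume that 20% to 50% of patients have ISR and that half of those respond. Exact 95% intervals for response in the ISR cell are:

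| Group | ISR cell | 95% CI |
|---|---|---|
| Placebo | 4 | 7-93% |
| Placebo | 10 | 19-81% |
| Pooled PSL | 8 | 16-84% |
| Pooled PSL | 20 | 27-73% |

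By stratum it is worse: "A minimum of 6 patients must be enrolled in each stratum, but the remaining patients can be enrolled in either stratum". At that minimum, with equal allocation, a stratum has 6/3 = 2 patients per arm before any split by ISR.

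**6. The two definitions of ISR.** Sections 3.3.6 and 3.4.2 share the threshold (50%) and the reference (Baseline dose). Section 3.4.2 adds only which drugs count. An analyst building one ISR flag would use the fuller text.

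**7. Cuts before Baseline.** "All medications, including transplant immunosuppression, used within 30 days before screening will be recorded", so recent cuts can be traced. Randomisation balances earlier ones in expectation.

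**The case for a change.** The strongest case is that the protocol itself makes the link matter. BK viremia is the key secondary endpoint, and the synopsis attaches a superiority hypothesis to it. Protocol 4.2 also says the study should find the dosing interval that lowers viral load in recipients who stay on immunosuppression, yet no planned table shows response in patients whose doses were not cut. A cross-count would use a flag the SAP already defines, and fixing the order of ISR and response beforehand would remove a choice that might otherwise be made after unblinding.

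Part of this stands. The table is absent, and the relative timing of ISR and response is the one rule not written down. But Protocol 9.1 plans no formal hypothesis testing, and the SAP's efficacy analyses are descriptive. Protocol 9.4.5 does mention one-sided comparisons, but a randomised as-observed contrast is valid with or without a test. Response and ISR are each defined in advance, and viral loads and dose changes are listed by patient. Blinding (Protocol 6.3) and a common ISR guideline (Appendix 7) limit investigator-driven differences between arms. A response-by-ISR table would compare groups formed after randomisation by the outcome itself, so it could not isolate a drug effect under continued immunosuppression.

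One limit of the review copy: the columns of SAP Table 1 are broken, so the population for the ISR row cannot be read there. The default in SAP 3.4 is ITT, and the row carries no restriction to patients below 10,000 copies/mL.

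**Conclusion.** No change to the plan is needed. It is true that no planned summary joins BK response to ISR across all patients. Following the SAP still gives a correct answer to the question it poses: PSL plus permitted care against placebo plus permitted care. The ISR row in Table 1 goes further than the optional summary promised in Protocol 6.8 and would reveal an imbalance between arms.

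The possible understatement of a no-ISR effect is 1 to 16 points of response, or 0.03 to 0.20 log10 in the mean. It rests wholly on assumed rates and on an equal ISR effect in both arms, and it vanishes or reverses under other assumptions. Counting ISR as failure would exchange that for a shift that can favour PSL. A plain cross-count is harmless but too imprecise at 20 patients per arm to settle attribution, and it can be drawn from defined items if a reader wants it. The missing drug list in SAP 3.3.6 is a drafting slip that 3.4.2 resolves.
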